2.0 Objectives

2.1 Primary Objective(s)

2.1.1 To determine the in-field control of hypofractionated radiotherapy consisting of 70 Gy in 25 fractions without concurrent chemotherapy measured at two years after the first post-radiotherapy scan.

2.2 Secondary Objective(s)

- 2.2.1 To determine the toxicity profile of thoracic HRT consisting of 70 Gy in 25 fractions as graded by CTCAE version 5.0
- 2.2.2 To determine proportion with local, regional, and distant progression at 1 and 2 years after the first post-radiotherapy scan, and compute progression-free and overall survival (PFS and OS, respectively).

3.0 Patient Selection

3.1 Inclusion Criteria

- 3.1.1 Histological confirmation of non-small cell lung cancer by either biopsy or cytology
- 3.1.2 AJCC 8th Edition Stage II-III or ultracentral Stage IB disease as determined by PET/CT and MRI Brain
 - 3.1.2.1 Ultracentral disease will be defined as edge of gross visible tumor within 1cm of the proximal bronchial tree
- 3.1.3 ECOG Performance Status of 0-3
- 3.1.4 Patient is not eligible for or has declined surgical resection or SBRT as determined by the treating physician
- 3.1.5 Patient is not eligible for or has declined concurrent chemotherapy as determined by the treating physician
 - 3.1.5.1 While we expect it to be an uncommon event, sequential use of systemic therapy after completion of RT is permissible if the patient's status improves such that they become eligible for such therapies, per the discretion of a multidisciplinary tumor board.
- 3.1.6 Negative serum or urine pregnancy test within 2 weeks of the date of enrollment for women of child-bearing potential
- 3.1.7 Ability to understand and the willingness to sign an IRB-approved informed consent document (either directly or via a legally authorized representative).

3.2 Exclusion Criteria

- 3.2.1 History of previous thoracic radiotherapy with the exception of prior radiotherapy for breast cancer without overlap of the fields with the cancer to be treated
- 3.2.2 Prior systemic therapy or surgery for the study cancer
- 3.2.3 Prior malignancy within the past two years except for non-melanoma skin cancer, prostate cancer, or any in-situ malignancy
- 3.2.4 Receipt of anti-angiogenic therapy, such as bevacizumab, within 6 months of enrollment
- 3.2.5 Pregnant women are excluded from this study because radiation therapy has known potential for teratogenic or abortifacient effects.

3.3 Inclusion of Women and Minorities

Men and women of all races and ethnicities who meet the above-described eligibility criteria are eligible to participate in this study. The study consent form will also be provided in Spanish for Spanish-speaking participants.

Based on WFBCCC population estimates, we may expect approximately 44% of participants to be women. Translating this to our sample size estimate of 43, we may enroll approximately 19 women. We may enroll approximately 10-13% Black or African American. Based on our catchment area and hospital demographics we do not expect accruals of individuals of Hispanic/Latino, American Indian/Alaska Native or Asian ancestry; however, no individual will be excluded from the study if they satisfy the above inclusion/exclusion criteria. Should we not meet or exceed these estimates, the PI will engage the Office of the Center for Health Equity to discuss strategies to enhance recruitment in these target populations.

4.0 Registration Procedures

All patients entered on any WFBCCC trial, whether treatment, companion, or cancer control trial, **must** be linked to the study in EPIC within 24 hours of Informed Consent. Patients **must** be registered prior to the initiation of treatment.

Contact Information:

Protocol Registrar [contact]

Protocol Registrar [contact]

Protocol Registrar E-MAIL ([contact])

*Protocol Registration is open from 8:30 AM - 4:00 PM, Monday-Friday.

You must perform the following steps in order to ensure prompt registration of your patient:

- 1. Complete the Eligibility Checklist (Appendix A)
- 2. Complete the Protocol Registration Form (Appendix B)
- 3. Alert the Cancer Center registrar by phone, *and then* send the signed Informed Consent Form, Eligibility Checklist and Protocol Registration Form to the registrar, either by fax or e-mail.
- 4. Fax/e-mail ALL eligibility source documents with registration. Patients **will not** be registered without all required supporting documents. Note: If labs were performed at an outside institution, provide a printout of the results. Ensure that the most recent lab values are sent.

To complete the registration process, the Registrar will:

- Assign a patient study number
- Register the patient on the study

5.0 Study Outcomes and Study Measures

5.1 Primary Outcome

5.1.1 The primary outcome measure will be presence/absence of any in-field progression by 2 years. In-field progression is defined as growth of the targeted lesions beyond the treated volume. The treated volume will be defined as the 28.75 Gy isodose line (50% of 57.5 Gy). Pathologic confirmation of tumor progression is preferred, but can be determined radiographically by Multidisciplinary Thoracic Oncology Program consensus if biopsy of the lesion in question is not feasible or safe.

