5.2 Secondary Outcomes

- 5.2.1 Toxicities will be evaluated per CTCAE Version 5.0 one month following completion of therapy and then every 3 months thereafter until 25 months from completion of radiation therapy.
- 5.2.2 Patterns of progression will be defined as follows: Local progression will be defined as in field progression (see Section 5.1.1); regional progression will be defined as any new regional lymphadenopathy in the hilum or mediastinum that was not included in the gross tumor volume (GTV); distant progression will be defined as any radiographic or pathologic evidence of disease outside the primary tumor and regional lymph nodes, including subsequent pulmonary parenchymal lesions. Progression-free survival will be evaluated by considering the time from registration to progression of disease or death; those who do not experience either outcome will be censored at date of last visit. Overall survival will be evaluated by considering the time from registration to death from any cause; those who do not die will be censored at date of last visit. Progression will be assessed through CT scans administered immediately following treatment and then every 3 months after that, out to 25 months.

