- vii. PTV 6750 = PTV 7000 minus PBT 1cm
 - PTV_6750 will only be delineated in cases where dose constraints for the PBT cannot be met
- d. Organs at Risk to be contoured
 - i. For all patients
 - 1. Bilateral lungs
 - 2. Spinal cord (5 cm above and below the PTV)
 - 3. Aorta (5 cm above and below the PTV)
 - 4. Esophagus (entire length)
 - 5. Esophagus PRV = Esophagus plus 5mm uniform expansion
 - 6. Heart (including the pericardial sac)
 - 7. Trachea/proximal bronchial tree
 - a. 5 cm superior to the PTV to the end of all main lobar bronchi
 - 8. PBT_PRV = trachea and proximal bronchial tree plus 5mm uniform expansion
 - ii. For patients with the PTV within 2 cm of the organ at risk*
 - 1. Brachial plexus
 - a. Only the major trunks of the brachial plexus need to be contoured
 - b. Left and right brachial plexuses should be contoured separately with generation of separate Brachial_Plexus_PRVs if the PTV is within 2 cm of both brachial plexuses
 - 2. Brachial_Plexus_PRV = Brachial plexus plus 5mm uniform expansion
 - 3. Chest wall (3 cm superior and inferior to the PTV)
 - 4. Ribs
 - 5. Stomach
 - 6. Liver
 - * if non-coplanar beams or arcs are used then all organs at risk must be contoured For patients who cannot meet PBT dose constraints
 - 1. PBT_1cm = trachea and proximal bronchial tree plus 1 cm uniform expansion iv.
 - Target Coverage Requirements
 - i. Mandatory
 - 1. 95% of PTV 5750 to at least 95% of prescription (54.63 Gy)
 - 2. 99% of PTV 5750 to at least 90% of prescription (51.75 Gy)
 - ii. Ideal

iii.

- 1. 95% of PTV 7000/6750 to at least 95% of prescription (66.5 Gy/64.13 Gy)
- 2. 100% of PTV 7000/6750 to at least 95% of prescription (66.5 Gy/64.13 Gy)
- 3. 95% of PTV_7000/6750 to at least 100% of prescription (70 Gy/67.5 Gy)
- 4. 99% of PTV 7000/6750 to at least 90% of prescription (63 Gy/60/75 Gy)
- 5. 100% of PTV 5750 to at least 95% of prescription (54.63 Gy)

- f. Organ at Risk Constraints
 - i. Mandatory
 - 1. Spinal Cord: $D0.03 \text{ cm}^3 < 45 \text{ Gy}$
 - 2. Esophagus: $D0.03 \text{ cm}^3 < 73.5 \text{ Gy}$;
 - 3. Lungs-GTV: V20 Gy \leq 35%;
 - 4. Proximal Bronchial Tree: D0.03 cm 3 < 73.5 Gy; D3 cm 3 < 66.25
 - 5. Heart D100% < 30 Gy
 - 6. Stomach: $D0.03 \text{ cm}^3 < 60 \text{ Gy}$
 - 7. Liver: Mean dose < 30 Gy; at least 700 cm³ of normal liver to < 15 Gy
 - 8. Maximum physical dose < 115% of high dose prescription
 - a. PTV_7000: maximum physical dose < 80.50 Gy
 - b. PTV 6750: maximum physical dose < 77.63 Gy

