8.0 Measurement of Effect

8.1 Antitumor Effect – Solid Tumors

Response and progression will be evaluated in this study using the Response Evaluation Criteria in Solid Tumors (RECIST) criteria 1.1. Changes in the largest diameter (unidimensional measurement) of the tumor lesions and the shortest diameter in the case of malignant lymph nodes are used in the RECIST criteria.

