11.2 Analysis of Secondary Objective

- 11.2.1 We will compute the proportion of the sample developing any toxicity of grade 2 or higher over the 25 months, and construct a corresponding 95% confidence interval.
- 11.2.2 We will compute proportions of patients who have experienced local progression by 13 months (1 year following first post-radiotherapy scan) and by 25 months (2 years following first post-radiotherapy scan), and will also compute the same two proportions considering regional progression, distant progression, and any (of the 3 categories) progression. We will construct 95% confidence intervals around these proportions. Those patients for whom we are unable to determine progression status at 1 and 2 years (e.g., because they do not return for the necessary scans, or because they die without evidence of progression) will be left out of these analyses. We will evaluate PFS and OS first using the Kaplan-Meier lifetable method, and will estimate median survival and corresponding 95% CIs; we will also explore simple Cox proportional hazards models of each of these survival outcomes, to examine the predictive influence of variables such as age, gender, ECOG performance status, stage at diagnosis, PTV 7000+6750 volume, and PTV 5750 volume. Patients who are lost to follow-up will be censored at that time in these analyses.

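### Section 5.1.1 defines in-field progression as growth beyond the treated volume, so regrowth inside the field is, as written, not a primary event

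*Combined protocol and SAP*

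**What the plan says.** The primary objective (2.1.1) is "To determine the in-field control of hypofractionated radiotherapy consisting of 70 Gy in 25 fractions without concurrent chemotherapy". Section 5.1.1 makes the outcome the presence or absence of in-field progression by 2 years and gives its only operational definition: "In-field progression is defined as growth of the targeted lesions beyond the treated volume". It continues: "The treated volume will be defined as the 28.75 Gy isodose line (50% of 57.5 Gy"). Pathology is preferred. Where biopsy is not feasible or safe, the multidisciplinary thoracic programme decides radiographically by consensus.

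Other sections that bear on the event:

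- 5.2.2, local: "Local progression will be defined as in field progression (see Section 5.1.1").
- 5.2.2, regional: new hilar or mediastinal nodes that were not in the GTV.
- 5.2.2, distant: "distant progression will be defined as any radiographic or pathologic evidence of disease outside the primary tumor and regional lymph nodes".
- 11.2.2 reports local progression, and then the same proportions "considering regional progression, distant progression, and any (of the 3 categories) progression".
- 8.1: "Response and progression will be evaluated in this study using the Response Evaluation Criteria in Solid Tumors (RECIST) criteria 1.1". It sets no isodose condition.
- 6.1.1, mandatory coverage: "99% of PTV 5750 to at least 90% of prescription (51.75 Gy").
- Appendix P records local progression as yes or no and gives no definition.

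**The concern.** The event is named for failure inside the field, but its definition requires growth out of the field. Taken literally, a treated lesion that regrows within the 28.75 Gy line is scored as controlled. The regional and distant definitions do not pick it up either, so it also disappears from the combined any-progression proportion in 11.2.2.

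Section 11.0 says the primary aim is the only hypothesis-testing analysis. If assessors follow the text, true failures are missed and the error favours the treatment. If they follow ordinary meaning or RECIST, the reported endpoint is not the one in the protocol. If practice is mixed, the control rate has no single meaning.

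The benchmark comparison is also affected. Section 11.3.1 does not say how the series behind the 0.50 figure defined in-field failure, so it cannot be shown that like is compared with like.

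**Working it through.** **Where the line lies.** 28.75 / 57.5 = 0.50, so the stated 50% is right; it is 28.75 / 70 = 41% of the high dose. PTV_5750 is the iGTV plus 5 mm (CTV_5750), plus a further 5 mm; the CTV may be trimmed at uninvolved structures (6.1.1). Mandatory coverage puts 99% of PTV_5750 at 51.75 Gy or more. Since 51.75 > 28.75, at least 99% of that target lies inside the line.

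**Which category catches regrowth inside the line (5.2.2)?**

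| Category | Requirement | Met? |
|---|---|---|
| Local | Growth past the 28.75 Gy line | No |
| Regional | New nodes not in the GTV | No |
| Distant | Disease outside the primary and regional nodes | No |

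**The plan's own figure.** Inputs from 11.1.1 and 11.3.1: null 0.50, alternative 0.75, one-sided α 0.05, 80% power, one-sample z-test. Using the null variance:

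n = ((1.645 + 0.842) × 0.5 / 0.25)² = 24.7, rounded up to 25.

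This reproduces the stated n. Allowing 15% missing, 25 / 0.85 = 29.4, rounded up to 30, which matches planned recruitment. Correcting the definition changes none of these inputs.

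**Decision threshold.** With k patients controlled of 25, z = (k/25 − 0.5) / √(0.25/25) = (k/25 − 0.5) / 0.1.

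- k = 16: z = 1.40, below 1.645, not rejected.
- k = 17: z = 1.80, rejected.

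The test therefore succeeds at 17 or more. Counted correctly, this rule has exact type I error 0.054 and power 0.851.

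**Unscored failures needed to reach 17.**

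| True controlled | True failures | Left unscored to reach 17 |
|---|---|---|
| 16 | 9 | 1 |
| 15 | 10 | 2 |
| 14 | 11 | 3 |
| 13 | 12 | 4 |

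**Sensitivity range.** Let m be the share of true in-field failures that stay inside the line and go uncounted. The documents do not give m, so it is varied. With true control 0.50, recorded control is p = 1 − 0.5(1 − m) = 0.5 + 0.5m, and the chance of success is P(X ≥ 17) for X ~ Binomial(25, p).

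| m | p | P(declare success) |
|---|---|---|
| 0 | 0.500 | 0.054 |
| 0.05 | 0.525 | 0.087 |
| 0.1 | 0.550 | 0.134 |
| 0.2 | 0.600 | 0.274 |
| 0.3 | 0.650 | 0.467 |
| 0.4 | 0.700 | 0.677 |
| 0.5 | 0.750 | 0.851 |

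The probability reaches 0.10 at m = 0.065 and 0.20 at m = 0.153. At m = 0.5, a regimen no better than the historical control would show the 75% the trial hopes for.

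**The case against.** The strongest reply is that the word for beyond is a drafting slip. The endpoint's name, objective 2.1.1 and the wording of 11.3.1 all point to the ordinary meaning, and events are settled by pathology or multidisciplinary consensus. Nothing shows that those assessors would call in-field regrowth controlled; if they would not, m is 0. This may well be so, but it is a reason to correct the text. The consensus step governs how an event is established when biopsy is not possible; it does not change what counts as one.

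Other points stand in part:

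- Objective 2.1.1 does not define in-field control, so the clash there is one of terms. Section 8.1 is a general rule that could coexist with a location-specific event; what is missing is a statement of how they relate. The firm conflict is inside 5.1.1 itself.
- The probabilities are conditional on literal scoring, on true control of exactly 50% (the protocol hopes for 75%) and on an m with no source. The one-patient example also supposes a result at the cut-off: at true control of 50%, exactly 16 of 25 occurs about 6% of the time (0.115 − 0.054 = 0.061). Any misclassification moves a threshold test this small. The feature specific to this wording is that literal errors all run in one direction.
- The Introduction describes a randomised study in elderly patients that counted recurrence within the treated volume as failure. That study is not shown to be the source of the 0.50, for which 11.3.1 cites other references. It supports only a request to state the benchmark's definition.
- Regrowth that meets RECIST may still enter progression-free survival, since tumour measurements are taken at each follow-up. This limits the loss for that secondary outcome but does not help the primary one.

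**Conclusion.** The concern holds and must be fixed. The only operational definition of the only tested endpoint excludes the failures it is named for, and following it as written would score some true in-field failures as control. The direction is certain under literal scoring: apparent control can only rise. The size is not known. It runs from no bias, if assessors ignore the wording, to a false-success probability of 13% at m = 0.1, 27% at m = 0.2 and 85% at m = 0.5. Those figures assume 25 evaluable patients, true control of 50%, the z-test cut-off of 17, and an illustrative m. The sample size is unaffected. That the text is wrong as written rests on none of these assumptions.

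**What to change.** 1. Reword 5.1.1, for example: *In-field progression is progression of a targeted lesion within, or arising within, the treated volume (28.75 Gy isodose line), whether or not it later extends past that line. Disease arising outside the line is not in-field.* Keep the existing sentence on pathology and consensus. It is useful here because 9.1.3 warns that collapsed lung can be reported as progression.
2. The local progression definition in 5.2.2 refers to 5.1.1 and will follow; check that the three categories then cover all progression.
3. State in 8.1 how the RECIST 1.1 result, a sum of diameters on Appendix Q, relates to the primary event, including what amount of growth counts and which rule governs if they differ.
4. Print the definition on Appendix P.
5. In 11.3.1, confirm that the series behind the 0.50 benchmark used the same definition, or state the difference.

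The cost is a short amendment and one line on a form. No new scans, data or patients are needed, and the plan stays at 25 evaluable and 30 recruited. Any patients already assessed are re-read from existing scans and plans. The reported control rate may be less favourable.

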5.2 Secondary Outcomes

- 5.2.1 Toxicities will be evaluated per CTCAE Version 5.0 one month following completion of therapy and then every 3 months thereafter until 25 months from completion of radiation therapy.
- 5.2.2 Patterns of progression will be defined as follows: Local progression will be defined as in field progression (see Section 5.1.1); regional progression will be defined as any new regional lymphadenopathy in the hilum or mediastinum that was not included in the gross tumor volume (GTV); distant progression will be defined as any radiographic or pathologic evidence of disease outside the primary tumor and regional lymph nodes, including subsequent pulmonary parenchymal lesions. Progression-free survival will be evaluated by considering the time from registration to progression of disease or death; those who do not experience either outcome will be censored at date of last visit. Overall survival will be evaluated by considering the time from registration to death from any cause; those who do not die will be censored at date of last visit. Progression will be assessed through CT scans administered immediately following treatment and then every 3 months after that, out to 25 months.

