6.0 Treatment Plan

6.1 Study-Related Activities

Activity	Pre- Study ^a	Prior to First Fraction of RT	At Each Weekly Treatment Visit on RT	1 month after RT completion	Every 3 months after 1 month post-RT scan until 25 months after RT ¹
Informed consent	X				
Demographics	X				
Medical history	X			X	X
Concurrent meds	X				
Physical exam	X			X	X
Vital signs ^g	X			X	X
Height ^d , Weight, ^g	X			X	X
Performance Status ^g	X		X	X	X
Tumor measurements ^e	X			X	X
B-HCG ^b	X				
FDG PET/CT Skull Base to Mid Thigh ^j	X				
MRI Brain with contrasti	X				
CT Chest/Abdomen ^c				X	X
Adverse event evaluation ^f Mandatory target coverage/dose constraint	X	X	X	X	X
compliance ^k				: 121:	

^a Pre-study requirements listed in table must be completed within 12 weeks prior to registration.

^b Serum or urine pregnancy test (women of childbearing potential). This must be completed within one week prior to initiation of radiotherapy for women of childbearing potential. For our purposes postmenopausal women are defined as women over the age of 45 years old with at least 12 months from their date of last menstruation.

^c CT Chest/Abdomen will be with contrast unless the patient has a documented contraindication to IV CT contrast (ie inadequate renal function or anaphylaxis). The scan must include the entire bilateral lungs, liver, and bilateral adrenal glands. CT Chest/Abdomen/Pelvis is also acceptable.

^d Height measured at pre-study only

e See Appendix Q

f See Appendices F and G

g See Appendix L

^h See Appendix C

¹ If MRI is contraindicated, CT Head with contrast is also acceptable.

^j National guidelines indicates a PET scan is good for 3 months (12 weeks).

^k See Appendix N

¹For all follow-up imaging and clinic follow-up time points above, a flexibility window of +/- 8 weeks is allowed.

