7.0 Dosing Delays/Dose Modifications

7.1 Any Grade 3 or higher acute toxicity with the exception of hematologic and laboratory toxicity may result in a treatment break at the discretion of the treating investigator until it resolves to Grade 2 or less. Duration of treatment break is at the discretion of the treating radiation oncologist. All labs will

be assessed by the treating physician to determine whether they are considered clinically significant or not clinically significant and treatment will be held at their discretion.

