9.1.2 Gastrointestinal/Esophageal Injury

9.1.2.1

The radiation effects on the esophagus can be acute: esophagitis (i.e., dysphagia, causing pain on swallowing, typically relatively soon after RT course is completed, and typically resolves on its own within days to a week or longer), or chronic, typically manifesting with dysphagia due to stenosis, or esophageal ulceration, with perforation in the extreme cases. The stomach and small bowel are also susceptible to radiation injury that manifests as nausea, anorexia, and vomiting (acute) or stenosis, ulceration, or rarely perforation (late). The liver is exquisitely sensitive to radiation therapy. Acute manifestation of liver toxicity is usually reflected by increasing hepatic enzymes (AST and ALT), as well as nausea. Late radiation hepatotoxicity is extraordinarily rare when treating intrathoracic malignancies, as large amounts of the liver can be irradiated to high doses as long as an adequate volume of liver is spared and the mean dose is kept below 30 Gy (see Section 6.2.1).

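### Read as written, the grade 2+ toxicity proportion omits events that arise and resolve during the roughly five weeks of radiotherapy, although the weekly visits already record them

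*Combined protocol and SAP*

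**What the plan says.** Objective 2.2.1 is to determine the toxicity profile of the regimen under CTCAE version 5.0. It is not limited to the period after treatment.

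Section 5.2.1 is the only definition of the corresponding outcome. It reads "Toxicities will be evaluated per CTCAE Version 5.0 one month following completion of therapy and then every 3 months thereafter", and this continues "until 25 months from completion of radiation therapy". It names no evaluation during radiotherapy.

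Section 11.2.1 gives the analysis: "We will compute the proportion of the sample developing any toxicity of grade 2 or higher over the 25 months", with a 95% confidence interval. It does not state when the 25 months begin.

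Other sections deal with the treatment period. The schedule in 6.1 has a column headed "At Each Weekly Treatment Visit on RT", and the adverse event row is marked in it, with a pointer to Appendices F and G. Appendix F records the CTCAE grade and the start and end dates of each event. Section 7.1 states: "Any Grade 3 or higher acute toxicity with the exception of hematologic and laboratory toxicity may result in a treatment break".

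**The concern.** The objective covers the whole regimen and on-treatment events are collected, but the outcome definition names only evaluations after treatment. An analyst who follows 5.2.1 and 11.2.1 literally would report a grade 2+ proportion without toxicity that appeared and settled during the course. That could include an event severe enough to interrupt treatment under 7.1.

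This proportion is the only toxicity summary named in section 11. A reader of the results would naturally take it as the rate for the regimen as a whole. The plan should therefore settle, before the data are seen, whether on-treatment events count.

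**Working it through.** The plan gives no figure to reproduce here. The check sets the sections side by side and works out the length of the uncovered period.

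**1. Where the clock starts.**
- Section 5.2.1 counts its 25 months from completion of radiotherapy.
- Section 11.2.1 uses the same length without a start.
- Section 11.2.2, on progression, uses "by 25 months (2 years following first post-radiotherapy scan". The schedule in 6.1 places that first scan 1 month after radiotherapy, so 25 − 24 = 1 month, and month 0 is again the end of radiotherapy.

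Section 11.2.2 does not govern toxicity, but it supports reading the 25 months in 11.2.1 the same way. No section says that weekly on-treatment events enter the proportion.

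**2. How long the uncovered period is.**
- Treatment: 25 fractions / 5 per week = 5 weeks (6.1.1). If every week had only 4 fractions, it would be 25 / 4 = 6.25 weeks. Treatment breaks would add to either figure.
- First fraction to the first named evaluation: 5 + about 4 = about 9 weeks.
- The Appendix G follow-up form asks about the previous 30 days. At an on-time 1-month visit this reaches back to about the end of radiotherapy and covers the last 4 of those 9 weeks.
- Uncovered: about 9 − 4 = 5 weeks, which is the treatment period itself.

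An event that starts on treatment and is still grade 2 or higher after it ends can be picked up. The events at issue are those that resolve within the course.

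**3. Direction.** Let A be the number of patients with a grade 2+ event counted after radiotherapy, and B the number whose only grade 2+ events arose and resolved during it. The proportion as written is A/n. The proportion for the whole regimen is (A + B)/n. Since B ≥ 0, the first cannot exceed the second.

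**4. Size, as an illustration only.** The documents give no acute grade 2+ rate, so the rates here are assumptions. Take n = 30 (11.3.1) and suppose 30% have a grade 2+ event counted after radiotherapy. Let a fraction *a* of the remaining 70% have one during treatment only. The rate for the whole regimen is then 0.30 + 0.70 × *a*. Intervals are exact (Clopper-Pearson), with counts rounded to whole patients.

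| Assumed *a* | Rate | Count | Exact 95% CI |
|---|---|---|---|
| 0 (as written) | 0.30 | 9/30 | 14.7% to 49.4% |
| 0.10 | 0.37 | 11/30 | 19.9% to 56.1% |
| 0.20 | 0.44 | 13/30 | 25.5% to 62.6% |
| 0.40 | 0.58 | 17/30 | 37.4% to 74.5% |

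Under these assumptions the shortfall is 2, 4 or 8 patients in 30, that is about 7, 13 or 27 percentage points.

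**The case against.** The strongest reply is that no section excludes on-treatment events. Section 5.2.1 lists evaluation times and sets no onset window, 11.2.1 gives no start, the objective has no time limit, and Appendix F holds grades and dates for the whole course. An analyst could reasonably count everything in the log. This stands in part: a deliberate exclusion cannot be inferred. But the one outcome definition names only post-treatment evaluations and dates its 25 months from completion, so counting the weekly events means going beyond the text.

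Three stronger readings are tempting, and the documents do not support them.

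- *Acute esophagitis would be missed.* Section 9.1.2 says that it "typically resolves on its own within days to a week or longer", which may suggest that it clears before the first evaluation. The same sentence places typical onset shortly after the course is completed. The 30-day look-back at an on-time 1-month visit largely covers that period, and 6.4 requires at least 30 days of adverse event follow-up, by telephone if no visit takes place. The 8-week visit tolerance in 6.1 weakens the look-back for late visits but does not remove the requirement in 6.4.
- *Nine weeks are uncovered.* That is the time to the first named evaluation. With the look-back, about five weeks remain.
- *The window prevents comparison with the absence of grade 3+ acute esophagitis in the institutional series.* A pooled proportion of any grade 2+ toxicity could not be set against that figure whatever its start date.

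It is also fair to say that toxicity is a descriptive secondary outcome with no comparator and no test.

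**Conclusion.** The point holds as a gap between the outcome definition on one side and the objective and schedule on the other. Followed literally, 5.2.1 and 11.2.1 leave out toxicity that arises and resolves during about 5 weeks of treatment. The omission can only lower the reported grade 2+ proportion or leave it unchanged. How far cannot be determined from the documents.

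The conclusion rests on two readings. One is that the 25 months in 11.2.1 are those of 5.2.1. The other is that the weekly mark in the 6.1 schedule belongs to adverse event evaluation. In the available text that row runs together with the dose-constraint row, but this is the most natural reading of the weekly mark.

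A reader might infer a gap in patient safety. There is none: weekly evaluation, committee reporting during treatment and for 30 days after it (9.3 and Appendix D), and the halting rule in 11.6 all apply regardless of 5.2.1. This is a cheap improvement to an outcome definition.

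**What to change.** In 5.2.1 and 11.2.1, state that the toxicity window runs from the first fraction to 25 months after the last fraction, and that the weekly on-treatment evaluations recorded in Appendix F count towards the grade 2+ proportion. Reporting the on-treatment or acute part separately from the later part would help readers but is optional.

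The cost is a sentence in each of two sections. No visit, procedure or form is added, because the schedule already calls for these data. The one downside is that the reported toxicity rate may come out somewhat higher.
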